4.5 Participant Completion/ Withdrawal procedures

If a participant withdraws from the study before Week 18, an early withdrawal visit will be scheduled to conduct the week 18 assessments (24-hour urine, symptom assessment, hearing assessment, acceptance assessment, pill count, and return of study drug). Patients who stop taking study medication are not considered early withdrawals and will be asked to continue to provide follow-up data on the study schedule and to participate in the final study visit at week 18.

5 STUDY EVALUATIONS AND MEASUREMENTS

5.1 Measurements

All study evaluation and measurements will occur at study visits that occur at the time of routinely scheduled HD treatments at the patient's usual outpatient dialysis clinic. *Section 4.4* describes the timing and frequency of the measurements.

Baseline measurements

Complete medical history and clinical data: The participant's medical history will be taken from the EHR and confirmed verbally with the patient. The medical history will include a review of co-morbid conditions, medications, recent laboratory results (electrolytes, albumin, complete blood count, Kt/V, iron stores, bone-mineral tests), and dialysis treatment data (BPs (systolic and diastolic), weights (pre- and post-HD), UF volumes/rates, dialysate composition (sodium, potassium, bicarbonate, calcium), dialysate and blood flow rates, and vascular access type.

Serum blood tests: The following tests will be assessed via blood samples: sodium, potassium, chloride, urea, creatinine, magnesium, calcium, albumin and serum furosemide level. An additional 2.5 mL blood sample will be drawn, frozen, and stored in UNC Kidney Center -80° freezers for future testing as needed. Blood samples will be collected via the vascular access by trained dialysis clinic personnel.

24-hour urine collection: The following tests will be assessed via 24-hour urine collections: urine volume, sodium, urea, creatinine, and urine furosemide level. An aliquot of urine will be taken from the sample after the before-listed measurements are performed and be frozen and stored in UNC Kidney Center -80° freezers for future testing as needed. Urine samples will be collected by the patient in 24-hour urine collection containers. Containers will be provided by and returned to study staff at the dialysis clinic at specified study visits.

Symptom assessment: Study staff will administer a symptom questionnaire (*Appendix, Section 13.1*) to participants at specified study visits.

Hearing assessment: Study staff will administer the Inner Ear instrument (*Appendix, Section 13.2*) to participants at specified study visits.

Follow-up measurements

Serum blood tests: The following tests will be assessed via blood samples: sodium, potassium, chloride, urea, creatinine, magnesium, calcium, albumin and serum furosemide level. An additional 2.5 mL blood sample will be drawn, frozen, and stored in UNC Kidney Center -80° freezers for future testing as needed. Blood samples will be collected via the vascular access by trained dialysis clinic personnel.

24-hour urine collection: The following tests will be assessed via 24-hour urine collections: urine volume, sodium, urea, creatinine, and urine furosemide level. An aliquot of urine will be taken from the sample after the before-listed measurements are performed and be frozen and stored in UNC Kidney Center -80° freezers for future testing as needed. Urine samples will be collected by the patient in 24-hour urine collection containers. Containers will be provided by and returned to study staff at the dialysis clinic at specified study visits.

Symptom assessment: Study staff will administer a symptom questionnaire (*Appendix, Section 13.1*) to participants at specified study visits.

Hearing assessment: Study staff will administer the Inner Ear instrument (*Appendix, Section 13.2*) to participants at specified study visits.

Pill counts: Study staff will perform pill counts at specified study visits.

Acceptance assessment: Study staff will ask participants the following yes/no/unsure question: "If recommended, would you be willing to stay on the dose of furosemide you have received during the last week?"

Clinical data: The following data will be obtained from the EHR: HD treatment BPs (systolic and diastolic), weights (preand post-HD), UF volumes/rates, dialysate composition (sodium, potassium, bicarbonate, calcium), dialysate and blood flow rates, and vascular access type.

5.2 Specimen preparation, handling and storage

All blood samples (2.5 mL tubes) will be collected via the vascular access by HD staff. Samples will be transported (on the day they are drawn by study staff) to UNC McClendon Laboratories and UNC Hostetter Laboratory for processing and storage (extra sample) at -80°C in UNC Kidney Center freezers (5th floor Burnett-Womack building). 24-hour urine samples will be collected in 24-hour urine jugs provided by and returned to study staff at the dialysis clinic. Urine samples will be transported to UNC McClendon Laboratories and UNC Hostetter Laboratory on ice for processing. Following processing, an aliquot of urine will be taken from the sample after the before-listed measurements are performed and be frozen and stored in UNC Kidney Center -80° freezers.

6 STATISTICAL CONSIDERATIONS

The short-term endpoints will be measured in the 6-week dose titration period (period 1). The longer-term endpoints will be measured in the 12-week follow-up period (period 2).

6.1 Primary Endpoints

Short-term and longer-term efficacy- urine volume (assessed separately)

- Among participants with baseline 24-hour urine volume ≥200 mL: incidence of ≥25% increase in urine volume
- Among participants with baseline 24-hour urine volume <200 mL: incidence of a ≥50 mL increase in urine volume to a urine volume of at least 100 mL/24-hours

Short-term and longer-term safety- electrolytes (assessed separately)

- Incidence of serum potassium <3.2 mEq/L
- Incidence of serum magnesium <0.8 mg/dL
- Incidence of serum corrected calcium <7.0 mg/dL

Short-term and longer-term safety- furosemide levels

• Incidence of serum furosemide level >12 microgram/L

Short-term and longer-term safety- BP

 Incidence of dialysis-associated hypotension requiring hospitalization or treatment in an emergency room and not attributable to overt sepsis, acute myocardial infarction, or other cardiovascular event (e.g. aortic dissection)²¹

Short-term and longer-term safety- symptoms (assessed separately)

- Incidence of severe or very severe patient-reported rash, tinnitus, or hearing change) not attributable to causes
 other than furosemide
- Incidence of 10-point decrease in Inner EAR instrument score

Short-term and longer-term tolerability- symptoms (assessed separately)

• Incidence of severe or very severe patient-reported cramping, dizziness/pre-syncope, unusual tiredness/weakness, chest pain, nausea, vomiting, or diarrhea not attributable to causes other than furosemide

Short-term and longer-term acceptability

• Incidence of an affirmative response to the furosemide acceptance question

Short term- and longer-term adherence

• Incidence of participants having <20% of furosemide pills remaining at pill counts

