2.1 Primary Objectives

Period 1 (dose escalation = short-term outcomes; 6-weeks) and Period 2 (follow-up = longer-term outcomes; 12-weeks)

Short-term and longer-term efficacy: To test the hypothesis that furosemide will increase 24-hour urine volume at its maximally tolerated dose in individuals with HD-dependent ESKD. 24-hour urine volumes will be used as the primary endpoint for both short-term and longer-term efficacy assessments.

Short-term and longer-term safety: To evaluate the short-term (6-weeks) and longer-term (12-weeks) safety of escalating doses of furosemide in individuals with HD-dependent ESKD. Safety outcomes will include the following:

- Serum potassium level <3.2 mEq/L
- Serum magnesium level <0.8 mg/dL
- Serum corrected calcium level <7 mg/dL
- Serum furosemide level >12 microgram/L
- Serious dialysis-associated hypotension defined as hypotension requiring hospitalization or treatment in an emergency room and not attributable to overt sepsis, acute myocardial infarction, or other cardiovascular event (e.g. aortic dissection)
- Severe or very severe rash, tinnitus, or hearing change not attributable to causes other than furosemide
- Inner EAR score decrease by ≥10 points

Short-term and longer-term tolerability: To evaluate the short-term and longer-term tolerability of furosemide in individuals with HD-dependent ESKD. Tolerability will be assessed by:

• Severe or very severe cramping, dizziness/pre-syncope, unusual tiredness/weakness, chest pain, nausea, vomiting, or diarrhea not attributable to causes other than furosemide

Short-term and longer-term acceptability: To evaluate the short-term and longer-term acceptability of furosemide in individuals with HD-dependent ESKD. Acceptability will be assessed by:

- Participant affirmative response to question: "If recommended, would you be willing to stay on the dose of furosemide you have received during the last week?"
- Recruitment rates
- Drop-out rates

Short-term adherence: To evaluate short-term and longer-term adherence to furosemide among individuals with HDdependent ESKD. Adherence will be assessed by:

- Pill counts
- Serum and urine furosemide levels

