6.2 Exploratory Endpoints

Short-term and longer-term efficacy- alternative definitions (assessed separately)

- Absolute change in urine volume from baseline (continuous in mL urine)
- Percentage change in urine volume from baseline (continuous in %)

Short-term and longer-term safety- electrolytes- alternative definitions (assessed separately)

- Absolute change in serum potassium from baseline (continuous in mEq/L)
- Absolute change in serum magnesium from baseline (continuous in mg/dL)
- Absolute change in serum corrected calcium from baseline (continuous in mg/dL)
- Percentage change in serum potassium from baseline (continuous in %)
- Percentage change in serum magnesium from baseline (continuous in %)
- Percentage change in serum corrected calcium from baseline (continuous in %)

Short-term and longer-term safety- BP- alternative definitions (assessed separately)

- Incidence of intradialytic systolic BP <80 mmHg²¹
- Incidence of intradialytic systolic BP <90 mmHg⁴¹
- Lowest systolic BP during HD (continuous in mmHg)

Short-term and longer-term acceptability alternative definitions (assessed separately)

- Number (percentage) of participants withdrawing from the study
- Number (percentage) period 1 participants not continuing to period 2

Short-term and longer-term adherence alternative definitions (assessed separately)

- Number (percentage) of furosemide tablets not taken (# tablets remaining/# tablets provided)
- Serum furosemide level (continuous in microgram/L and binary, present vs. absent)
- Urine furosemide level (continuous in microgram/L and binary, present vs. absent)

Clinical endpoints (assessed separately)

- Change in 24-hour creatinine clearance from baseline (continuous in ml/min/1.73m²)
- Percentage change in 24-hour creatinine clearance from baseline (continuous in %)
- Change in 24-hour fractional excretion of sodium from baseline (continuous in %)

- Change in 24-hour fractional excretion of urea from baseline (continuous in %)
- Percentage change in 24-hour fractional excretion of urea from baseline (continuous in %)
- Pre-HD systolic BP (mmHg on a per-HD treatment basis)
- IDWG (kg on a per-HD treatment basis)
- UF volume (mL on a per-HD treatment basis)
- UF rate (mL/h/kg on a per-HD treatment basis)
- Target weight achievement (post-HD weight (kg) within 1kg of prescribed target weight) (binary on a per-HD treatment basis)

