Analogous to the primary analyses, percentage change measures, change measures, and value measures will be analyzed via one-way repeated measures of analysis of variance to determine the presence of absence of dose-related differences. In addition, we will use mixed effects modeling to test the effect of increased dose and duration with the fixed effect of time (dose), random subject effect, and an unstructured repeated covariance type. We will use generalized estimating equations to assess categorical outcomes. We will also consider binary outcomes as rates (events/time). Distribution of the exploratory parameters will be examined and appropriate transformation will be applied. These analyses are considered hypothesis-generating, and we will examine directionality and strength of relationships but will not assess via p-values.

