6.4 Sample Size and Power

We designed this pilot study to evaluate the safety, tolerability, and acceptability of furosemide use in HD patients and assess for furosemide efficacy and safety signals. We aim to enroll a sufficient number of participants to yield data supporting the efficacy, acceptability, tolerability, and safety of furosemide and to provide a basis for calculating the sample size of a future randomized trial. Sample size considerations were framed using standard study design parameters to ensure 80% power to detect pre-specified effect sizes utilizing intermediate outcomes.

With a sample size of 36 patients, we have 83% power to detect a mean change in urine volume from baseline of at least 5 ml/24-h, assuming a change S.D. = 10 ml/24-h¹⁷ and a 2-sided α = 0.05 (>99% power for urine volume change of 10 mL/24-h). With 30 patients, we have 99% power to detect a mean change in urine volume from baseline of at least 10 mL/24-h. Sample size calculation estimates were based on existing data about expected response to furosemide and S.D.s observed in other studies of urine volume in HD patients.¹⁷

Our goal sample size is 36 participants. We will account for dropout by enrolling up to 40 participants. If fewer than 30 participants are eligible for period 2 at the end of the period 1 dose titration period (i.e. participants who did not

tolerate or accept furosemide in period 1), we will recruit additional participants to maintain a sample size over 30 participants for the follow-up period.

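### The power in 6.4 is for a mean change in 24-hour urine volume, but primary efficacy in 6.1 is a responder rate needing a rise of at least 50 mL, and 6.3.4 leaves the scale unsettled

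*Combined protocol and SAP*

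**What the plan says.** **Objective (2.1).** The efficacy hypothesis is that furosemide raises 24-hour urine volume at the maximally tolerated dose, and "24-hour urine volumes will be used as the primary endpoint for both short-term and longer-term efficacy assessments".

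**Primary endpoint (6.1).** Volume becomes a yes/no outcome in two strata. In the upper stratum it is "Among participants with baseline 24-hour urine volume ≥200 mL: incidence of ≥25% increase in urine volume". Below 200 mL it is "incidence of a ≥50 mL increase in urine volume to a urine volume of at least 100 mL/24-hours". No clinical, guideline or regulatory reason is given for these cuts.

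**Primary analysis (6.3.4).** The efficacy measure is tagged as binary, and a sufficient rise in urine volume is assigned to generalized estimating equations. The same section also names 24-hour urine volume among the measures for one-way repeated-measures ANOVA and mixed models, which are methods for continuous data.

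**Exploratory endpoints (6.2, 6.3.5).** The list includes "Absolute change in urine volume from baseline (continuous in mL urine". For this class of endpoint, "we will examine directionality and strength of relationships but will not assess via p-values".

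**Sample size (6.4).** The figures are "83% power to detect a mean change in urine volume from baseline of at least 5 ml/24-h" with 36 patients, an SD of change of 10 mL/24 h and two-sided alpha 0.05; ">99% power for urine volume change of 10 mL/24-h"; and 99% power for 10 mL with 30 patients. No responder rate, reference rate, precision or power is given for the 6.1 endpoint.

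**The concern.** The quantity that was sized (6.4) and the quantity declared primary (6.1) are on different scales, and the effect and SD used for the first imply almost no events on the second. A reader who takes 83% as the power of the primary efficacy endpoint is misinformed. The continuous change, which matches both the hypothesis in 2.1 and the calculation in 6.4, is listed as exploratory, while 6.3.4 seems to give it a primary role as well. As written, two analysts could each follow the plan and report different primary efficacy results. One of the study's stated aims is to provide a basis for sizing a later randomized trial, so the primary scale should be clear.

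**Working it through.** **Inputs.** From 6.4: n = 36 and 30; mean change 5 or 10 mL/24 h; SD of change 10 mL/24 h; two-sided alpha 0.05. From 6.1: the two responder rules. From 3.2: one arm, everyone treated.

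**1. Reproduce the plan's power.** One-sample t-test on change, with noncentrality = (mean/SD) × √n and n − 1 degrees of freedom.
- n = 36, 5 mL: 0.5 × 6 = 3.0, power 83.1% (stated 83%).
- n = 36, 10 mL: 1.0 × 6 = 6.0, power 99.99% (stated above 99%).
- n = 30, 10 mL: 1.0 × 5.48 = 5.48, power 99.96% (stated 99%).

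The figures are right for a mean change.

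**2. Smallest rise that counts as a response.**
- Baseline 200 mL or more: 0.25 × 200 = 50 mL at the stratum edge, and larger above it (0.25 × 500 = 125 mL at a baseline of 500 mL).
- Baseline below 200 mL: 50 mL by definition, and more if baseline is under 50 mL, because the final volume must reach 100 mL.

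The floor is 50 mL in both strata.

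**3. Distance from the sized effect to the floor**, (50 − mean)/SD.
- 10 mL: (50 − 10)/10 = 4.0 SD.
- 5 mL: (50 − 5)/10 = 4.5 SD.
- At a baseline of 500 mL the gap is (125 − 10)/10 = 11.5 to (125 − 5)/10 = 12 SD.

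**4. Expected responders if change is normal**, at the 50 mL floor.
- 10 mL: upper tail beyond 4.0 SD = 3.2 × 10⁻⁵; × 36 = 0.0011.
- 5 mL: upper tail beyond 4.5 SD = 3.4 × 10⁻⁶; × 36 = 0.0001.
- The chance of no responder among 36 is 99.89% and 99.99%.

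**5. Without normality.** Cantelli's bound on the tail is 1/(1 + k²), with k the distance in SDs.
- k = 4.0: 1/17 = 5.9%, at most 2.1 of 36.
- k = 4.5: 1/21.25 = 4.7%, at most 1.7 of 36.

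**6. If the SD is larger.** The SDs above 10 mL are assumptions, not in the documents. Mean change 10 mL, n = 36, normal change, 50 mL cut.

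| SD of change (mL) | Responders | Expected of 36 | Crossing 50 mL if mean change is 0 | Power for the mean change |
|---|---|---|---|---|
| 10 (6.4) | 0.003% | 0.001 | <0.001% | 99.99% |
| 20 | 2.3% | 0.8 | 0.6% | 83.1% |
| 50 | 21.2% | 7.6 | 15.9% | 21.5% |
| 100 | 34.5% | 12.4 | 30.9% | 9.0% |

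Responders become common only at SDs where the 6.4 power has gone. At those SDs many participants would also cross the cut with no mean change, and the plan gives no reference rate for its single arm.

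**7. Source of the SD.** Section 6.4 cites reference 17 and speaks of studies in hemodialysis patients. Table 1 (Section 1.3) lists reference 17 as a peritoneal dialysis trial, and the text of 1.3 gives its mean volumes at randomization as 1,020 and 1,040 mL. Sections 1.1 and 1.3 also attach number 17 to a 13-patient hemodialysis study that Table 1 numbers 36. The documents do not settle which study supplied the 10 mL.

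**The case against.** **The 5 and 10 mL are detectable minima, not forecasts.** This stands. A reader might infer that the trial will end with no responders. The documents do not support that: 6.4 says at least 5 or 10 mL, a larger true effect would yield responders, and the near-zero count depends on the SD of 10 mL and near-normal changes.

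**Continuous analysis is not shut out.** This stands too. A reader of 6.2 and 6.3.5 might infer that the continuous change carries no inferential weight. But 6.3.4, under primary analyses, names 24-hour urine volume for ANOVA and mixed models, and the no-p-value rule sits only in 6.3.5. The defect is a contradiction, not an outright exclusion.

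**A low responder count would not be reported as proof of no effect.** Correct. Section 6.3.1 puts the emphasis on point and interval estimates and calls non-significant results inconclusive (though it prints that threshold as 0.5 after setting significance at 0.05). Section 6.3.7 adds sensitivity analyses with other outcome definitions.

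**A responder question is legitimate here.** Section 1.3 describes a diuretic threshold that differs between patients, which makes it sensible to ask who responds, though it does not justify the particular cuts. Nor can one infer that the continuous analysis is always more powerful. Assume a 15% average rise, n = 36 and a between-person SD of log response of 0.3. An exact test of the responder rate against its chance rate then beats a paired test on log volume by 93% to 60%, 70% to 51% and 39% to 36%, at single-collection CVs of 15%, 20% and 30%.

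None of this gives the 6.1 endpoint the power stated in 6.4, or settles which scale is primary.

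**Conclusion.** The point holds as a mismatch between sizing and endpoint, together with an internal contradiction on scale. On 6.4's own effect and SD, with roughly normal changes, the responder floor is 4.0 to 4.5 SD above the sized mean, and 0.0001 to 0.001 responders are expected among 36 (at most about 2 without normality). The stated 83% and 99% or more describe the mean change only. Raising the SD does not reconcile the two: at an assumed 50 mL and a 10 mL mean, 21.2% respond but power for the mean change is 21.5%.

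The near-zero count is conditional on 6.4 and does not predict the trial's result. The advantage of the continuous scale claimed here is that it matches 2.1 and 6.4, not that it has greater power in general. This should be corrected before analysis. It does not affect conduct or data collection.

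**What to change.** - **6.1 and 6.3.4:** make the continuous change in 24-hour urine volume from the week -1 baseline the primary efficacy analysis. Use the mixed model already planned, and give the estimate, 95% CI and p-value separately for short-term and longer-term. Remove the binary tag from this measure.
- **6.2:** move absolute change out of the exploratory list, so that the rule in 6.3.5 no longer applies to it.
- **Responder proportion:** keep the 25% / 50 mL definition as a secondary measure with an exact CI.
- **6.4:** state that the power refers to the mean change, recheck the SD of 10 mL, and correct its citation if needed. If the SD proves larger, restate the power.

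**Cost.** Wording only: both quantities come from urine collections already scheduled. The downside is that the headline becomes a mean change in mL, with the responder percentage second.

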Occurrence of any of the following events will end dose up-titration: 1) electrolyte abnormalities (serum potassium <3.2 mEq/L, serum magnesium <0.8 mEq/L, and/or serum corrected calcium <7 mg/dL); 2) side effects attributable to furosemide (severe or very severe rash, tinnitus, or hearing change); decrease in Inner Effectiveness of Auditory Rehabilitation (Inner EAR) instrument score by more than 10 points; and/or intradialytic systolic BP <80 mmHg that a study investigator attributes to study drug-induced hypovolemia); and/or 3) patient non-acceptance (defined as the

patient reporting unwillingness to take the study drug). If one of these events occur, the participant will return to the prior tolerated oral furosemide dose. If one of these events occurs at the lowest administered dose, oral furosemide will be stopped and not re-started.

During the 12-week follow-up period (period 2), participants who tolerated and accepted furosemide in period 1 will continue their maximally tolerated period 1 furosemide dose during the 12-weeks of follow-up. If a participant has electrolyte abnormalities or other side effects attributable to furosemide in period 2 (i.e. on their period 1 maximally tolerated dose), the dose will be lowered sequentially (i.e. dose de-escalation: $160 \rightarrow 120 \rightarrow 80$ mg twice daily, or, if on alternative dosing due to prior diuretic use, decrease dose by 50%, rounded to the nearest whole tablet strength of existing (i.e. available) furosemide tablet formulations, until tolerated). If side effects persist or if the participant chooses, oral furosemide will be stopped.

Investigational New Drug (IND) exemption status

Oral furosemide is marketed as a prescription drug product and regulated by the U.S. FDA. Furosemide is indicated for edema and hypertension (signs and symptoms of volume overload). Its use in this study will be considered an on-label use. Our study is exempt from IND requirements for the following reasons:

- Oral furosemide is lawfully marketed in the U.S.
- The study is not intended to be reported to the FDA as a well-controlled study in support of a new indication for use and is not intended to be used to support any other significant change in the labeling for the drug.
- The study is not intended to support a significant change in the advertising for the product.

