1.3.1. Risks

Risks of furosemide include electrolyte abnormalities (hypokalemia, hypomagnesemia, and hypocalcemia), hypotension, allergic or toxicity-related symptoms (rash, tinnitus, and hearing change), and other symptoms (cramps, dizziness, unusual tiredness/weakness, chest pain, nausea, vomiting, diarrhea, and numbness/tingling). Furosemide-induced ototoxicity can lead to transient or permanent deafness. Ototoxicity primarily occurs with high-dose intravenous therapy (e.g. >240 mg/hr infusions) or at lower doses in patients with kidney function impairment or concurrent use of other ototoxins such as aminoglycosides.

We have chosen our study selection criteria to exclude patients who are at increased risk for furosemide side effects including those with frequent hypotension, cirrhosis, a hearing disorder, or electrolyte abnormalities in the prior 30 days (hypokalemia defined as serum potassium <3.5 mEq/L, hypomagnesemia, defined as serum magnesium <1 mg/dL, and hypocalcemia, defined as serum corrected calcium < 8 mg/dL), and those taking an interacting drug or substance including an aminoglycoside, cisplatin, methotrexate, cyclosporine, adrenocorticotropic hormone (ACTH), lithium, phenytoin, oral/intravenous steroid, or natural licorice.

In the current trial, risks related to furosemide will be reduced through close monitoring of serum electrolytes, patient symptoms (including hearing), BP, and serum and urine furosemide levels. In addition, we will withdraw participants from the study if any of the following occurs during the course of the study: 1) pregnancy; 2) initiation of a non-loop diuretic (spironolactone, eplerenone, ethacrynic acid, thiazides); 3) initiation of an interacting drug (aminoglycoside, methotrexate, cyclosporine, ACTH, lithium, phenytoin, or oral/intravenous steroid); and/or 4) new diagnosis of cirrhosis.

Occurrence of any of the following events will end dose up-titration (defined below): 1) electrolyte abnormalities, 2) side effects attributable to furosemide (e.g. hypotension, allergic or toxicity-related symptoms), and/or 3) patient non-acceptance. If one of these events occur, the participant will return to the prior tolerated furosemide dose. If one of these events occurs at the lowest administered dose, furosemide will be stopped and not re-started.

- Serum potassium <3.2 mEq/L
- Serum magnesium <0.8 mEq/L
- Serum corrected calcium <7.0 mg/dL

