7.3.2. Trial-Defined Adverse Events

The HD population undergoes frequent laboratory testing and has a high rate of peri-dialytic hypotensive events requiring changes in the dialysis prescription, adjustment of estimated dry (target) weight, or change in dialysis-related medications. Due to the unique nature of this population, the following events are considered routine aspects of maintenance HD therapy and will not be recorded as an AE except as noted:

- Anemia will be reported when hemoglobin is <7.5 mg/dL
- Hypokalemia will be reported when potassium level <3.2 mEq/L
- Hyperkalemia will be reported when potassium level ≥6.6 mEq/L
- Hypomagnesemia will be reported when magnesium level <0.8 mEq/L
- Hyperphosphatemia will be reported when phosphorous >9.5 mg/dL

- Hypocalcemia will be reported when serum corrected calcium <7.0 mg/dL
- Hypercalcemia will be reported when serum corrected calcium >11.0 mg/dL
- Hyperparathyroidism will be reported when PTH >1200 pg/mL
- Hypotension will be reported when it meets the criteria for serious dialysis-associated hypotension (hypotension requiring hospitalization or treatment in an emergency room and not attributable to overt sepsis, acute myocardial infarction, or other cardiovascular event (e.g. aortic dissection))
- Hearing change will be reported if Inner EAR score decreases by 10 points from baseline
- Tinnitus- will be reported at level of severe or very severe patient-reported tinnitus
- Rash- will be reported at level of severe or very severe patient-reported rash

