7.1.2 Hypomagnesemia management

Serum magnesium will be measured weekly during dose escalation and monthly during follow-up. Treating clinicians will manage the dialysate magnesium according to clinic standards. Study staff will monitor magnesium values and contact treating clinicians in the event of hypomagnesemia to ensure that hypomagnesemia is being actively managed. Treating clinicians will be free to manage hypomagnesemia according to local standards, including changes to the dialysate magnesium concentration. However, study drug dose reductions or discontinuation will be directly managed by study investigators. Occurrence of a serum magnesium <0.8 mEq/L will end dose titration, and the participant will return to the prior tolerated furosemide dose. If the hypomagnesemia occurs at the lowest administered dose, furosemide will be stopped and not restarted. Serum magnesium will be rechecked within one week when magnesium is <0.8 mEq/L. Results of serum magnesium will be conveyed to treating clinicians and the dialysis unit nursing staff.

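### The magnesium safety endpoint is <0.8 mg/dL, but the dosing and adverse event rules say <0.8 mEq/L, which is 0.97 mg/dL

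*Combined protocol and SAP*

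**What the plan says.** The endpoint is in mg/dL. Section 6.1 lists "Incidence of serum magnesium <0.8 mg/dL" among the primary safety endpoints, Section 2.1 gives "Serum magnesium level <0.8 mg/dL", and the synopsis agrees.

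The rules that act on a result are in mEq/L. The up-titration stop in Section 1.2 reads "serum magnesium <0.8 mEq/L", and the same number and unit recur in 1.3.1, 3.5.2 and 4.3. Hypomagnesemia management (numbered 7.1.2, under 7.7) states: "Occurrence of a serum magnesium <0.8 mEq/L will end dose titration, and the participant will return to the prior tolerated furosemide dose". That section uses the same cut-off for the one-week recheck, and it stops furosemide for good if the event occurs at the lowest dose given. Section 7.3.2 defines the adverse event: "Hypomagnesemia will be reported when magnesium level <0.8 mEq/L".

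Section 1.3.1 uses both units. Its account of the entry criteria has "hypomagnesemia, defined as serum magnesium <1 mg/dL"; its list of events that end titration has "Serum magnesium <0.8 mEq/L". The exclusion criterion in 3.4 and the exploratory magnesium change in 6.2 are in mg/dL. No text reconciles the two units.

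**The concern.** The number 0.8 appears with two units that are not interchangeable, so the threshold that changes dose is not the threshold that counts as a primary safety event. A coordinator following the dosing text and an analyst following Section 6.1 would classify the same result differently.

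What is at stake depends on which unit was intended.

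- **If mEq/L was intended**, some participants will have furosemide reduced or stopped for hypomagnesemia, and an adverse event recorded, without appearing in the primary hypomagnesemia endpoint. Under 7.5 the investigators watch the safety endpoints while the safety monitor may act on adverse events. For magnesium those would be two different counts.
- **If mg/dL was intended**, following the written rule ends titration, steps the dose down or stops the drug sooner than planned. Section 2.1 tests efficacy at the maximally tolerated dose, and that dose is carried into period 2. Stopping at the lowest dose also affects who is eligible for period 2, which under 6.4 governs further recruitment.

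**Working it through.** **1. Thresholds side by side**

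| Analyte | Entry floor (3.4) | Endpoint (synopsis, 2.1, 6.1) | Stop rule (1.2, 1.3.1, 3.5.2, 4.3) | Adverse event (7.3.2) | Management (7.7) |
|---|---|---|---|---|---|
| Potassium | 3.5 mEq/L | 3.2 mEq/L | 3.2 mEq/L | 3.2 mEq/L | 3.2 mEq/L |
| Corrected calcium | 8 mg/dL | 7.0 mg/dL | 7.0 mg/dL | 7.0 mg/dL | 7.0 mg/dL |
| Magnesium | 1 mg/dL | 0.8 **mg/dL** | 0.8 **mEq/L** | 0.8 **mEq/L** | 0.8 **mEq/L** |

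Only magnesium changes between the endpoint and the rules. Each unit recurs consistently within its own group of sections, so this is not a text-extraction fault.

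**2. Conversion.** Atomic weight 24.305 and valence 2 are physical constants, not taken from the documents.

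- Equivalent weight = 24.305 / 2 = 12.1525 mg per mEq.
- 0.8 mEq/L × 12.1525 / 10 = 0.972 mg/dL.
- In reverse, 0.8 mg/dL × 10 / 12.1525 = 0.658 mEq/L.
- Width of the discordant band: 0.972 − 0.800 = 0.172 mg/dL.
- Ratio: 0.972 / 0.8 = 1.215, so the stop threshold is about 22% higher.

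**3. Distance from entry floor to stop threshold**

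- Potassium: (3.5 − 3.2) / 3.5 = 8.6%.
- Calcium: (8 − 7) / 8 = 12.5%.
- Magnesium, if mg/dL: (1 − 0.8) / 1 = 20%.
- Magnesium, mEq/L as written: (1 − 0.972) / 1 = 2.8%, or about 0.03 mg/dL.

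Read literally, a participant can enter at 1 mg/dL and meet the stop rule after a fall of about 0.03 mg/dL.

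**4. Which reported results are discordant.** The laboratory's reporting unit and precision are not stated, so both cases below are assumptions.

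- Reported in mg/dL to 0.1: results of 0.8 and 0.9 trigger the rule but not the endpoint.
- Reported in mEq/L to 0.1: only 0.7 is discordant (0.7 × 1.21525 = 0.85 mg/dL). A result of 0.8 does not trigger the rule, and 0.6 (0.73 mg/dL) meets both.

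**5. Effect on incidence.** One participant in the band is 1/36 = 2.8 points at the period 1 target and 1/30 = 3.3 points at the period 2 figure. The number in the band cannot be derived from the documents. For illustration, assume 0 to 3 of 36 in the band and nobody below 0.8 mg/dL (exact Clopper-Pearson 95% intervals):

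| Participants in band | Endpoint as written | Dosing and adverse event rule as written |
|---|---|---|
| 0 | 0/36 (0 to 9.7%) | 0% (0 to 9.7%) |
| 1 | 0/36 (0 to 9.7%) | 2.8% (0.1 to 14.5%) |
| 2 | 0/36 (0 to 9.7%) | 5.6% (0.7 to 18.7%) |
| 3 | 0/36 (0 to 9.7%) | 8.3% (1.8 to 22.5%) |

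**6. Power.** The plan gives no calculation for magnesium. Its urine-volume power in 6.4 (n = 36, change 5 mL, SD 10 mL, two-sided 0.05) reproduces: noncentrality 5/10 × √36 = 3, which gives 83.1% by the paired t-test against 83% stated. It does not depend on the magnesium unit.

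**The case against.** The strongest reply is that this is a unit slip on the cautious side. All analysis-facing text (synopsis, 2.1, 6.1, 6.2) and the entry criteria agree on mg/dL, so the analyst has a clear instruction. The rule as written acts earlier, so nobody is exposed to lower magnesium than intended. Results in the band are still captured as adverse events of interest and as continuous change, so safety data are not lost. All of that stands, and it makes mEq/L the likelier error.

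It can also be argued that a stop rule stricter than its endpoint is legitimate, since the plan does this for hypotension: intradialytic systolic pressure below 80 mmHg attributed to the drug ends titration, while the endpoint requires hospitalization or emergency treatment. But there the plan writes out two different definitions. Here it repeats one number in another unit without comment, and the other two electrolytes show no such gap.

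Three limits are fair:

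- Section 6 plans no adverse event incidence table. Under 7.3.3 a repeat test can refute a laboratory adverse event, while the 6.1 endpoint has no confirmation rule, so the two counts could differ for any electrolyte even after the unit is fixed.
- The period 2 step-down text in 3.5.2 and 4.3 refers to electrolyte abnormalities without a number, so the mEq/L cut-off reaches it only by reference.
- The margin percentages in step 3 take no account of how variable each electrolyte is, which the documents do not give.

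None of these removes the conflict.

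**Conclusion.** The concern holds. The primary hypomagnesemia endpoint and the rules that change dose and define the adverse event differ by 0.172 mg/dL (0.800 against 0.972), and the plan gives no reason. The mismatch and the conversion are certain. Which unit was intended is not: the entry floor and the exploratory endpoint point to mg/dL, but that is inference.

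The practical effect depends on how many participants have a value in the band, which is unknown and may be zero. The effect on the maximally tolerated dose is therefore possible rather than shown. The conflict should still be fixed, because one written result can end titration or permanently stop the drug before any recheck.

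**What to change.** The clinical leads should confirm the intended threshold. It should then be given in the laboratory's reporting unit and used identically in the endpoint, stop, recheck and adverse event text.

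- **If mg/dL is intended:** change the magnesium unit in 1.2, 1.3.1, 3.5.2, 4.3, 7.3.2 and Hypomagnesemia management under 7.7. No analysis change is needed.
- **If mEq/L is intended:** set the endpoint in the synopsis, 2.1 and 6.1 to 0.97 mg/dL, or tabulate incidence at both 0.8 and 0.97 mg/dL, so that every event that triggers the rule is counted. Reconsider the 1 mg/dL entry floor, which leaves a margin of only 0.03 mg/dL.

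The cost is wording edits in six sections or three, plus one extra safety-table row only if both thresholds are tabulated. No new data collection is needed.

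A separate small edit, which adds no weight to this point, can go in at the same time. The Inner EAR stop rule in 1.2, 3.5.2 and 4.3 requires a fall of more than 10 points, while 2.1 and Ototoxicity management under 7.7 use 10 or more. Setting the stop rule to ≥10 aligns them.
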